## 7 INVESTIGATIONAL PRODUCT DISCONTINUATION AND PARTICIPANT DISCONTINUATION/WITHDRAWAL

### 7.1 Discontinuation of Study Medication

If the subject is discontinued from the study medication, the following 3 options are available: 1) taper off deflazacort; 2) in conversation with their healthcare provider, they could switch to a commercially available generic version of deflazacort; or 3) in conversation with their healthcare provider, they could switch to other commercially available corticosteroids.

Long term administration of deflazacort may lead to suppression of the hypothalamic-pituitary-adrenal (HPA) axis. Rapid reduction or abrupt withdrawal of therapy that has been prolonged or at high doses can cause secondary adrenal insufficiency (suppression of the HPA axis), and steroid withdrawal or deprivation syndrome. Recovery from suppression of the HPA axis after discontinuing deflazacort can be prolonged (possibly 6 to 12 months) and may vary based on doses, dosing schedules and duration of deflazacort therapy. Since there is a great deal of individual variability in susceptibility to suppression of the HPA axis after chronic use of exogenous corticosteroids, it is not possible to predict with confidence which subjects will be affected. Deflazacort should not be stopped suddenly. Therefore, general tapering recommendations are provided; however, investigators may taper according to their standard of care and clinical judgement. If there is no standard tapering practice at the site, the following taper practice based on the PJ Nicholhof Protocol ([Kinnett 2017](#)) is advised ([Table 5](#)):

1. Using the 6 mg tablet strengths from the available taper bottle, begin by giving a 20% to 25% lower dose for two weeks
2. Repeat step 1 and continue to lower the dose by 20% to 25% original dose until near physiologic dose (~0.1 mg/kg)
3. If necessary, substitute deflazacort with short acting form of a corticosteroid (ie, hydrocortisone (0.3 mg/kg/day))
4. Stop corticosteroids and observe for signs of adrenal crisis

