##### **6.1.2 Dosing and Administration**

Deflazacort will be assigned via an IRT system according to the subject's weight at baseline. Subjects will be assigned deflazacort 0.6 mg/kg/day and will continue on the assigned weight based dose through 26 weeks. Any subject assigned to placebo prior to the Version 4.0 amendment will be switched to deflazacort as described above.

Study drug will be taken by the subject orally, at home (except on days where the subject is instructed to take the dose in clinic), in a single, daily, morning dose. If the subject is unable to swallow the tablet whole, tablets may be crushed in between two spoons or using a tablet crusher

and stirred into soft food (eg, applesauce, pudding) and ingested immediately. Subject must be instructed not to split the tablet(s) and subjects are instructed not to chew the study drug. Tablets may be taken with or without water and with or without food.

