**Table 2. Weight-based Dosing Summary**

	Dose (mg)	Target Weight (in Kg)	Weight Band (in Kg)	Dosing Combination
0.6 mg/kg/day	24	40.0	35 - 49.9	6mg + 18mg
	36	60.0	50 -74.9	36 mg
	54	90.0	75 - 112.5	36mg + 18mg

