### 6.1.2.2 *Safety Criteria for Adjustment or Stopping Dosing*

Unless an occurrence of an AE requires otherwise, the investigator is encouraged to maintain the same dose through the first 13 weeks of treatment due to the potential to confound the PK, safety, and efficacy evaluations. Dose adjustments are permitted as follows:

1. In order to maintain the weight-based dose of 0.6 mg/kg/day of deflazacort, if the subject has experienced weight gain that places them in the next higher weight band, the dose may be increased accordingly. If the subject has experienced an AE as described below, the Investigator may elect not to increase the dose despite weight gain.
2. At the discretion of the Investigator, the dose may be decreased to that of the next lower weight band in response to an AE. See recommendations below.
3. At the end of the study, subjects will switch from the study medication to an appropriate dose of a commercially available deflazacort or any other available corticosteroid. If the subject/Investigator does not wish to continue corticosteroid use, the dose of deflazacort must be reduced per Section 7.1 procedures.

Discontinuation of deflazacort during Period 1 of the study should be avoided unless clinically necessary. In the case of the development of predictable, deflazacort-related adverse effects, appropriate supportive care should be provided such that dosage can be maintained. Specific, standard of care recommendations for precautionary interventions for specific corticosteroid-related AEs are given below.

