### **6.2.2 Formulation, Appearance, Packaging, and Labeling**

Deflazacort tablets (6 mg, 18 mg and 36 mg) will be used for this study. The tablets are white, and either round or ovular in shape depending on the strength of the tablet (6 mg and 18 mg tablets are round, 36 mg tablets are ovular). Tablets will be packaged in weekly blister cards. Weekly blister cards will be packaged into visit cartons. Tablets needed for appropriate taper dose will be available and packaged in bottles. The blister cards, visit cartons, and bottles will be labeled in accordance with participating country regulatory requirements and certified language text translation.

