**Table 5. Taper paradigm per weight band**

Weight Band (mg)	0.6 mg/kg Target Weight	1 st Reduction* (~.45 mg/kg)	2 nd Reduction* (~0.3 mg/kg)	3 rd Reduction* (~0.15 mg/kg)	Consider Short Acting Corticosteroid
24	40 kg	18 mg	12 mg	6 mg	Stop Deflazacort
36	60 kg	30 mg	18 mg	12 mg	Stop Deflazacort
54	90 kg	42 mg	30 mg	18 mg	Stop Deflazacort

\*Approximate mg/kg calculations based on the weight requirement to achieve exactly 0.6 mg/kg dose. 20% fluctuation (higher and lower weight) is inherent in each weight band and should be considered when applying the tapering paradigm.

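### Protocol Table 5 stops deflazacort from 0.20 mg/kg in the 36 and 54 mg rows, one step short of the taper end point in Section 7.1.

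*Protocol*

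**What the plan says.** Protocol Section 7.1 warns of adrenal suppression and states: "Deflazacort should not be stopped suddenly". Investigators may follow their own practice. Where a site has none, a four-step scheme and Table 5 are advised. Step 1 lowers the dose by 20% to 25% for two weeks, using 6 mg tablets. Step 2 tells the site to repeat this and to "continue to lower the dose by 20% to 25% original dose until near physiologic dose (~0.1 mg/kg". Step 3 allows a short-acting corticosteroid if necessary (hydrocortisone 0.3 mg/kg/day), and step 4 stops corticosteroids.

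Table 5 gives three reductions for each starting dose, headed about 0.45, 0.3 and 0.15 mg/kg, and then stops deflazacort. The stop column is headed as the point at which to consider a short-acting corticosteroid. The footnote gives the basis of the headings, "Approximate mg/kg calculations based on the weight requirement to achieve exactly 0.6 mg/kg dose", and adds that a "20% fluctuation (higher and lower weight) is inherent in each weight band and should be considered when applying the tapering paradigm".

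Tablet handling limits the possible doses. Section 6.1.2 says "Subject must be instructed not to split the tablet(s)", and Section 6.2.2 says "Tablets needed for appropriate taper dose will be available and packaged in bottles".

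**The concern.** The text and the table describe one taper but end it at different doses. A site with no practice of its own is the site most likely to read its row of Table 5 and follow it. For a subject on full dose weighing 50 to 112.5 kg, that row ends above both the dose named in step 2 and the table's own third-reduction heading. The last fall, to zero, is then larger than the step size the text allows. Section 7.1 itself says that susceptibility to adrenal suppression cannot be predicted for the individual subject, so the default instruction should name one stopping dose.

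**Working it through.** **Inputs.** Starting doses, target weights and bands come from Protocol "Table 2. Weight-based Dosing Summary": 24 mg (40 kg; 35 to 49.9), 36 mg (60 kg; 50 to 74.9), 54 mg (90 kg; 75 to 112.5). Taper doses come from Table 5. The step size of 20% to 25% and the end point of about 0.1 mg/kg come from Section 7.1.

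**1. How Table 5 was built.** Take 75%, 50% and 25% of the starting dose and round up to a multiple of 6 mg:

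| Start | 75% | 50% | 25% | Table 5 |
|---|---|---|---|---|
| 24 mg | 18 | 12 | 6 | 18, 12, 6 |
| 36 mg | 27 → 30 | 18 | 9 → 12 | 30, 18, 12 |
| 54 mg | 40.5 → 42 | 27 → 30 | 13.5 → 18 | 42, 30, 18 |

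All nine cells are reproduced.

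**2. Where the text's steps lead from 0.6 mg/kg.**
- 25% steps (0.15 each): 0.45, 0.30, 0.15, then 0. Last dose 0.15 mg/kg, final drop 25%.
- 20% steps (0.12 each): 0.48, 0.36, 0.24, 0.12, then 0. Last dose 0.12 mg/kg, final drop 20%.

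A fair benchmark is therefore a last dose of 0.12 to 0.15 mg/kg and a final drop of 20% to 25%.

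**3. Where Table 5 leads.** Last dose in mg/kg = last dose in mg / weight. Final drop = last dose / starting dose.

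| Start | At target weight | Heavy to light end of band | Final drop |
|---|---|---|---|
| 24 mg | 6/40 = 0.15 | 6/49.9 to 6/35 = 0.12 to 0.17 | 6/24 = 25% |
| 36 mg | 12/60 = 0.20 | 12/74.9 to 12/50 = 0.16 to 0.24 | 12/36 = 33.3% |
| 54 mg | 18/90 = 0.20 | 18/112.5 to 18/75 = 0.16 to 0.24 | 18/54 = 33.3% |

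The heading of about 0.15 is reproduced only in the 24 mg row. In the other two rows the excess over it at target weight is 12 − 9 = 3 mg and 18 − 13.5 = 4.5 mg, less than one tablet.

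**4. Does the weight footnote close the gap?** The last dose would be 0.1 mg/kg at 12/0.1 = 120 kg and 18/0.1 = 180 kg. The bands end at 74.9 and 112.5 kg. At the heavy end, 0.16 mg/kg agrees with the heading but still lies above the text's end point.

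**5. Subjects already reduced one band.** Section 6.1.2.2 says "the dose may be decreased to that of the next lower weight band in response to an AE". If such subjects then follow the lower row, they end at 12/112.5 to 12/75 = 0.11 to 0.16 mg/kg (54 to 36 mg) or 6/74.9 to 6/50 = 0.08 to 0.12 mg/kg (36 to 24 mg). The gap therefore concerns subjects on the dose for their own band.

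**6. One more step to 6 mg.**
- 36 mg row: step (12 − 6)/36 = 16.7%; 6/60 = 0.10 mg/kg (0.08 to 0.12 over the band); final drop 6/36 = 16.7%.
- 54 mg row: step (18 − 6)/54 = 22.2%; 6/90 = 0.07 mg/kg (0.05 to 0.08); final drop 6/54 = 11.1%.

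**The case against.** The best defence is that Table 5 is not miscalculated. One rounding rule explains every cell, tablets may not be split, and the headings are marked as approximate. This stands. A reader who sees 0.20 under a heading of 0.15 might infer an arithmetic slip, and the documents do not support that. Rounding does not explain, however, why the table stops at this point when the 6 mg tablets supplied allow a lower dose.

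A reader might also set 0.20 against exactly 0.1 mg/kg, and 33.3% against 0.1/0.6 = 16.7%, and call the stopping dose twice what was intended. That treats an approximate target as exact. The text asks only to come near it and gives no figure for the final drop. The benchmark in step 2 of the working is fairer, and a gap remains against it.

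The stop cell also sits under the short-acting steroid column, so the fall to zero need not be unbridged. That stands too, but the substitution is conditional. A reader might go further and infer that subjects were stopped abruptly or harmed. Nothing here shows that: the scheme is advisory, a site using it also has step 2 in front of it, and whether 0.20 rather than 0.12 to 0.15 mg/kg matters clinically cannot be judged from these documents.

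Finally, the 24 mg row runs up to 0.17 mg/kg at its light end, above the 0.16 at the heavy end of the other rows. That is true, but this row already ends on the lowest whole-tablet dose.

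**Conclusion.** The inconsistency between text and table is real, in two of three rows. For subjects on the dose for their own band, the 36 and 54 mg rows stop from 0.20 mg/kg at target weight, where the text's steps would end at about 0.12 to 0.15. At every weight in those bands the last dose exceeds 0.15 mg/kg. The final drop is 33.3% of the original dose, against a rule of 20% to 25%, if no short-acting steroid is given. The 24 mg row needs no change.

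This rests on reading the step size in Section 7.1 as governing the last step as well, and on the site following the table row as printed. Severity is minor. The taper is advisory, bridging is available, and SAP Section 6.9 counts treatment duration only to the last dose before tapering. No endpoint is affected, and SAP Section 1 reports 11 subjects enrolled.

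**What to change.** Add a fourth two-week reduction, to 6 mg, to the 36 and 54 mg rows of Table 5, and state that 6 mg tablets make the steps and the end point approximate.

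- **36 mg row, 12 to 6 mg.** The 16.7% step is a little below the rule. This cannot be avoided: 20% to 25% of 36 mg is 7.2 to 9 mg, which contains no multiple of 6.
- **54 mg row, 18 to 6 mg.** This repeats the 12 mg step the row already uses and stays within the rule. It ends below 0.1 mg/kg, because the exact dose at 90 kg (9 mg) cannot be made from 6 mg tablets. Stopping from 12 mg instead would give 12/90 = 0.13 mg/kg, but by a step of only 6/54 = 11.1%.

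If the clinical team intends to stop at 0.15 to 0.20 mg/kg, leave the rows alone and correct step 2 and the third-reduction heading.

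The first option lengthens the taper in these rows from about 3 × 2 = 6 weeks to 4 × 2 = 8 weeks, and the follow-up visit, timed from the last dose, moves with it. The second changes one line and one heading. Sites need notice only if a subject is still to be tapered.

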**Table 5. Taper paradigm per weight band**

Weight Band (mg)	0.6 mg/kg Target Weight	1 st Reduction* (~.45 mg/kg)	2 nd Reduction* (~0.3 mg/kg)	3 rd Reduction* (~0.15 mg/kg)	Consider Short Acting Corticosteroid
24	40 kg	18 mg	12 mg	6 mg	Stop Deflazacort
36	60 kg	30 mg	18 mg	12 mg	Stop Deflazacort
54	90 kg	42 mg	30 mg	18 mg	Stop Deflazacort

\*Approximate mg/kg calculations based on the weight requirement to achieve exactly 0.6 mg/kg dose. 20% fluctuation (higher and lower weight) is inherent in each weight band and should be considered when applying the tapering paradigm.

## 7.2 Participant Discontinuation/Withdrawal from the Study

If it is determined by the Investigator that any subject will discontinue the study, all early termination visit procedures should be completed and the final visit should be captured as early termination (ET) in an electronic case report form. If it is determined that a subject will discontinue the study in between visits, the subject should return at earliest convenience for an early termination visit, following completion of any required study medication assessments. The PTC medical monitor should be informed via e-mail of when a subject discontinues study treatment. For subjects who terminated early/discontinued from the study and are tapering off deflazacort, a follow-up visit will occur approximately 4 weeks after the final study drug dose. In case of discontinuation due to an AE, the AE should be followed up by the investigator until it is resolved, or the investigator assesses it as chronic or stable.

Reasons for discontinuation may be for any of the following reasons:

1. The subject requests to be discontinued from the study
2. The occurrence of a clinically significant worsening of disease status or change in a laboratory parameter that may place the subject at risk
3. Upon consultation with the PTC Therapeutics medical monitor, the Investigator may withdraw the subject from deflazacort treatment, if, in the Investigator's clinical judgment, it is not in the subject's best interest to continue.
4. The occurrence of a serious AE
5. The occurrence of a protocol violation, if it interferes with the safety of a subject or data integrity
6. The Sponsor or Investigator terminates the study

## 7.3 Lost to Follow-up

Subjects are considered lost to follow-up if the subject does not return to the clinic and attempts to contact the subject were unsuccessful. Efforts must be made on the part of the site to avoid any subject being lost to follow-up during the study. Before subjects are considered lost to follow-up, a minimum of 2 documented telephone contact attempts and 1 certified letter within 6 weeks of the most recent planned study visit must be sent in efforts to contact the subject. After being considered lost to follow-up, a subject's status may be changed if the subject makes contact at a later time provided the trial is ongoing.

## 8 STUDY ASSESSMENT AND PROCEDURES

### 8.1 Schedule of Events and Study Procedures

[Table 6](#) summarizes schedule of study procedures and assessments.

**Table 6. Schedule of Events**

Study Procedure	Screening 	Visit 1 	Safety Call	Visit 2	Visit 3 	Safety Call	Visit 4	Visit 5/ET 	Follow- up 	NOTES
Week (visit window)	-6 to -1 Weeks	Baseline / Week 1	Week 3	Week 13	Week 26	Week 28	Week 39	Week 52		
		(±1 weeks)	(±2 weeks)	(±2 weeks)	(±2 weeks)	(±2 weeks)	(±2 weeks)	(±2 weeks)		
Informed Consent	X									A signed and dated informed consent must be obtained before conducting any study procedures.
Inclusion/Exclusion	X	X								
Medical/Surgical History	X	X								
Demographics	X									
FKRP Genotyping	X									Samples will be collected for sequencing of the FKRP gene to confirm the presence of a mutation. Genetic testing for FKRP will not be performed if documentation of genetic diagnosis is available at screening.
Enrollment		X								The site will conduct initial subject registration in the IRT system at Screening. At Visit 1 (baseline), eligible subjects will be assigned dose via the IRT system.
Physical Exam	X	X		X	X		X	X		
Clinical Labs (Hematology  and Chemistry  )	X	X		X	X		X	X		Fasting approximately 8 hours prior to assessments.
Pregnancy Test 	X	X		X	X		X	X		All urine pregnancy tests taken at site will be confirmed by serum HCG. The urine pregnancy test must be negative prior to dispensation of study drug.
Height/Weight/BMI	X	X		X	X		X	X		For study inclusion, weight range must be ≥35 to ≤112.5 kg
Vitals (HR & BP)	X	X		X	X		X	X		
ECG	X			X	X			X		

Study Procedure	Screening 	Visit 1 	Safety Call	Visit 2	Visit 3 	Safety Call	Visit 4	Visit 5/ET 	Follow- up 	NOTES
Week (visit window)	-6 to -1 Weeks	Baseline / Week 1	Week 3 (±1 weeks)	Week 13 (±2 weeks)	Week 26 (±2 weeks)	Week 28 (±2 weeks)	Week 39 (±2 weeks)	Week 52 (±2 weeks)		
Echocardiogram	X									Echocardiograms obtained within 3 months of enrollment are sufficient to obviate the screening echocardiogram.
AE/SAE monitoring	X	X	X	X	X	X	X	X	X	
Concomitant Medications	X	X	X	X	X	X	X	X	X	Concomitant medications information will need to be collected starting 30 days prior to first dose of study drug.
Ophthalmic Exam 		X			X			X		Ophthalmic exams may be scheduled within 45 days of scheduled visit to accommodate scheduling restrictions.
Lateral Spine X-ray 		X			X			X		
DEXA 		X			X			X		
Columbia Suicide Rating Scale	X	X		X	X		X	X		
PK Blood Sampling 		X		X						PK samples will be drawn at Visit 1 and Visit 2 (steady state) for pharmacokinetic evaluation. The following PK parameters if possible, will be calculated using noncompartmental analysis method: AUC (0-t) , AUC (0-inf) , C max , T max , CL/F, Vz/F, λz, and t 1/2 . Samples will be drawn at pre-dose, and 0.5, 1, 2, 4, and 6 hours post-dose at baseline and Week 13 visits.
Timed Function Tests 	X	X		X	X		X	X		Timed function tests will be recorded and assessed centrally in addition to the site's clinical evaluator's assessment at the visit. Timed function tests include time to up and go, time to descend 4 stairs, time to climb 4 stairs, time to run/walk 10 meters, and 2-minute walk

Study Procedure	Screening 	Visit 1 	Safety Call	Visit 2	Visit 3 	Safety Call	Visit 4	Visit 5/ET 	Follow-up 	NOTES
Week (visit window)	-6 to -1 Weeks	Baseline / Week 1	Week 3 (±1 weeks)	Week 13 (±2 weeks)	Week 26 (±2 weeks)	Week 28 (±2 weeks)	Week 39 (±2 weeks)	Week 52 (±2 weeks)		
Hand Held Myometry 		X		X	X		X	X		test. Conduct details will be summarized in a manual separate from this protocol.
Pulmonary Function Testing 		X			X		X	X		Pulmonary function will be evaluated by spirometry. Pulmonary function test procedures will be detailed in a manual separate from this protocol. The following pulmonary function tests will be evaluated: FVC, MIP, and MEP.
Biomarker testing (Bone Health Assays) 		X		X	X			X		
INQoL Questionnaire 		X			X			X		
MRI 		X		X	X			X		Dixon MRI and T2 MRI will evaluate muscular fat fraction and inflammation, respectively, of selected lower limb muscles. Details will be further elucidated in an MRI manual separate from this protocol.
Study Drug Administration										
Dispense Drug via IRT		X		X	X		X			
Unused Drug Return/ Compliance				X	X		X	X	X 	

**Abbreviations:** AE, adverse event; BP, blood pressure; BMI, body mass index; DEXA; dual-energy X-ray absorptiometry; ECG, electrocardiogram; ET, early termination; FKRP, fukutin-related protein gene; FVC, forced vital capacity; HCG; human chorionic gonadotropin; HR, heart rate; INQoL, Individualized Neuromuscular Quality of Life; IRT, Interactive Response Technology; MEP, maximal expiratory pressure; MIP, maximal inspiratory pressure; MRI, magnetic resonance imaging; PD, pharmacodynamic; PK, pharmacokinetic; SAE, serious adverse event

**Note:** See also Section 3.4 for explanation of the transition from Protocol Version 3.0 to Version 4.0.

 Screening procedures must take place within 42 days of baseline visit (Visit 1). No study-related procedures should be performed prior to the signature of the

informed consent document(s).

-  Any screening procedure completed within and including 7 days of Visit 1, with the exception of the time to climb 4 stairs, can serve as baseline and does not need to be repeated at Visit 1. The time to climb 4 stairs must always be performed twice at the baseline visit and all other visits. The second 4 stair climb test should be done a minimum of 5 minutes after the prior test, or any other physical activity. The baseline visit may be split into two consecutive days.
-  At Visit 3, subjects initially randomized to deflazacort will continue deflazacort treatment while subjects originally randomized to placebo will initiate deflazacort treatment at a target dose of 0.6 mg/kg/day. For placebo subjects, all assessments will be performed prior to first dose of deflazacort (See also Section 3.4 for explanation of the transition from Protocol Version 3.0 to Version 4.0).
-  At Visit 5/ET, subjects/Investigators who elect to discontinue corticosteroid therapy altogether will need to taper off deflazacort. If it is determined by the Investigator that any subject will discontinue the study, all early termination visit procedures should be completed and the final visit should be captured as early termination (ET) in an electronic case report form (eCRF). If it is determined that a subject will discontinue the study in between visits, the subject should return at earliest convenience for an early termination visit, following completion of any required study medication assessments. For subjects who terminated early/ discontinued from the study and are tapering off deflazacort, a follow-up visit will occur approximately 4 weeks after the final study drug dose. In case of discontinuation due to an AE, the AE should be followed up by the investigator until it is resolved, or the investigator assesses it as chronic or stable.
-  The follow-up visit will be a phone call approximately 4 weeks after Visit 5 for subjects that complete the study and immediately start receiving commercial deflazacort or another corticosteroid. The follow-up will be an office visit for subjects that are tapering off deflazacort to return study drug and for site collection of any AEs and will occur 4-weeks after last dose of study drug.
-  Hematology assessments include hemoglobin, hematocrit, red blood cell count, mean corpuscular volume, mean corpuscular hemoglobin, and mean corpuscular hemoglobin concentration, mean platelet volume, red blood cell distribution width, neutrophils (% and absolute), total lymphocytes (% and absolute), monocytes (% and absolute), eosinophils (% and absolute), basophils (% and absolute), and platelets.
-  Chemistry assessments include sodium, potassium, chloride, bicarbonate, blood urea nitrogen (urea), creatinine, uric acid, protein (total), albumin, bilirubin (total), aspartate transaminase, alanine transaminase, gamma glutamyl transpeptidase, alkaline phosphatase, lactate dehydrogenase, glucose (fasting), hemoglobin A1c, calcium, phosphate, magnesium, creatine kinase, cholesterol, high density lipoproteins, low density lipoproteins (calculated), and triglycerides.
-  Only for women of child-bearing potential.
-  Ophthalmological examination includes a glaucoma assessment, cataract assessment, and intraocular pressure measurement.
-  If possible, both X-ray and DEXA should be performed; however, only an X-ray or DEXA is acceptable if the other technology is not available or prohibited per local ethical/regulatory decree.
-  The pre-dose blood draw will be taken within 2 hours before dosing. For timepoints up to 2-hours post dose, a window of  $\pm 10$  minute will be allowed for blood collection. From 4 hours to 6 hours post samples, a window of  $\pm 30$  minutes will be allowed.
-  Efficacy and PD assessments will be performed post-daily-dose at each clinic visit, except for the baseline visit (Visit 1). At screening and baseline visits, the ability to ascend 4 stairs must be  $\geq 2.5$  and  $\leq 8$  seconds. In addition, the 4-stair climb will be performed twice at each visit. The second test should be done a minimum of 5 minutes after the prior test (or any other physical activity). The two 4-stair climb results must be within 20% of one another. If they are not the Medical Monitor should be contacted.
-  Biomarker testing (bone health assays) include bone alkaline phosphatase (BAP), Beta-CrossLaps (Beta-CTx), insulin-like growth factor-1 (IGF1), parathyroid hormone (PTH) intact, aldosterone, and vitamin D (Serum 25-hydroxyvitamin D3).
-  INQoL will be performed before the first dose at baseline and after 26 weeks of treatment, when possible.
-  Dixon MRI and T2 MRI will be conducted at a subset of sites that have been pre-qualified by a central imaging vendor to perform this assessment. To be pre-qualified, a site must have access to whole-body scanner and appropriate personnel and must have been trained on the procedure for data acquisition. MRI data will be analyzed centrally.

